7.9.2 Pharmacodynamic Analysis

CCI

7.10 Other Outcomes

Not Applicable.

7.11 Safety Analysis

Safety analyses include adverse events (AEs), clinical laboratory parameters, vital sign parameters, and 12-lead electrocardiogram (ECG) results.

All summaries of safety data are based on subjects in the Safety Analysis Set.

7.11.1 Adverse Events

A treatment -emergent adverse event (TEAE) will be defined as an AE or serious adverse event (SAE) that started or worsened after first study drug administration and within 30 days of last dose of study drug (onset date – date of last dose + 1 ≤ 30). A TEAE will be attributed to a regimen if the TEAE occurs after administration of the study drug in a period and up to just prior to study drug administration in the next period. A TEAE that occurs after administration of the study drug in the last period and up to 30 days after the last study drug dose is attributed to the regimen received in the last period. All AE verbatim terms will be coded by system organ class (SOC) and preferred term using (PT) the MedDRA coding system.

TEAEs will be summarized by regimen (TAK-954 alone, itraconazole alone, and TAK-954 with itraconazole) and overall. The tables will include the number and percentage (N [%]) of subjects reporting any event for that term. The following TEAE tables will be summarized.

- Overview of TEAEs.
- TEAEs by SOC and PT at subject and event level.
- Subject Mappings for TEAEs.
- TEAEs by PT.
- Relationship of TEAEs to Study Drug by SOC and PT.
- Drug-Related TEAEs by SOC and PT.
- Severity of TEAEs by SOC and PT.
- Severity of Drug-Related TEAEs by SOC and PT.

In addition, pretreatment events (PTEs) will be summarized overall by SOC and PT.

For each regimen and overall, subjects reporting more than one occurrence for a term (SOC or PT) being summarized will be counted only once using the most extreme incident (most severe for the severity tables and related for the relationship to study drug tables).

Data listings will be provided for all TEAEs, PTEs, TEAEs that led to study discontinuation, TEAEs that led to abnormal liver functions, SAEs, AEs that resulted in death, and AEs occurring more than 30 days after the last dose of study medication.

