11.1.4 Safety Analysis

The safety set will be used for all summaries of safety parameters. These summaries will be presented by TAK-954 alone, itraconazole alone, and TAK-954 with itraconazole.

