4.2 Secondary Objectives

The secondary objectives of the trial are to evaluate the safety of single-dose IV doses of TAK-954 in the presence and absence of a potent CYP3A4 inhibitor.

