7.1.1 Study Definitions

There are no study-specific definitions.

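### The SAP assigns adverse events to regimens by period, so it cannot fill the itraconazole-alone column for any subject who receives the Period 2 infusion

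*SAP*

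**What the plan says.** SAP 7.11.1 defines a treatment-emergent event as one "that started or worsened after first study drug administration and within 30 days of last dose of study drug". It then assigns events to regimens: "A TEAE will be attributed to a regimen if the TEAE occurs after administration of the study drug in a period", lasting until just before dosing in the next period. For the final period, an event after dosing and "up to 30 days after the last study drug dose is attributed to the regimen received in the last period".

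The next paragraph of that section sets the table layout: "TEAEs will be summarized by regimen (TAK-954 alone, itraconazole alone, and TAK-954 with itraconazole) and overall". Protocol 11.1.4 has the same three columns: "These summaries will be presented by TAK-954 alone, itraconazole alone, and TAK-954 with itraconazole".

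The trial has two periods (SAP 4.4). Period 1 is a single TAK-954 infusion on Day 1. Period 2 is daily itraconazole on Days 1 to 8, with one TAK-954 infusion on Day 4 starting 1 hour after that day's itraconazole dose (Protocol 9.4). SAP 7.1.1 offers no help with terms: "There are no study-specific definitions".

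**The concern.** The tables need three regimens, but the rule has only two periods to work with and gives the last one a single label. Itraconazole alone and the combination are both Period 2 treatments. What separates them is the Day 4 infusion, and the attribution rule never refers to it.

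The secondary objective is "to evaluate the safety of single-dose IV doses of TAK-954 in the presence and absence of a potent CYP3A4 inhibitor". Its two sides are the combination column and the TAK-954-alone column. If events that began before any Period 2 TAK-954 are counted in either one, that column describes something other than its heading. The error would carry through every table by regimen in SAP 7.11.1, including the relationship and severity tables. The itraconazole-alone column, which would show what the inhibitor does by itself, would be empty for everyone who received the infusion.

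**Working it through.** The plan states no figure here to reproduce, so the check applies the written rule to the dosing timeline.

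**Inputs**
- Itraconazole once daily on Period 2 Days 1 to 8 (SAP 4.4, Protocol 9.4).
- Period 2 infusion on Day 4, 1 hour after itraconazole (Protocol 9.4).
- TEAE limit: onset date − last dose date + 1 ≤ 30 (SAP 7.11.1).
- Routine event collection to the Follow-up Visit, 10 to 14 days after the last dose (Protocol 10.2.9.1).
- About 10 subjects (SAP 6.0).

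**Interval at issue.** At nominal times, from the first itraconazole dose to the start of the infusion: 72 h (Day 1 to Day 4) + 1 h = 73 h, or 73/24 = 3.04 days. Itraconazole doses given by then: Days 1, 2, 3 and 4, so 4 of 8.

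**Period 2 TEAE window.** With the last dose on Day 8, onset ≤ 8 + 29 = Day 37. Days 1 to 37 are 37 × 24 = 888 h.

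**Labels for a subject who receives the infusion**

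| Rule | TAK-954 alone (Period 2 hours) | Itraconazole alone | Combination |
|---|---|---|---|
| As written, study drug = either drug | 0 | 0 | 888 |
| As written, study drug = TAK-954 only | 73 | 0 | 815 |
| Split at the infusion start | 0 | 73 | 815 |

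Here 888 − 73 = 815. The Period 2 split is the same for gaps of 7, 10 or 14 days between Period 1 Day 1 and Period 2 Day 1. Seven days is the documented minimum; 10 and 14 are assumptions. In the first row the combination label is inferred, as the natural value of the regimen received in a period that included both drugs. The SAP does not spell it out.

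**Subjects who leave Period 2 before the infusion.** If study drug means either drug, their last-period regimen is itraconazole alone, so only they could populate that column. If it means TAK-954 only, the column stays empty for them too.

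**Which reading is more natural.** The either-drug reading. Protocol 8.1 and 9.4 deal with itraconazole under trial drug, Protocol 9.5 treats Period 2 Day 1, an itraconazole-only day, as a trial-drug dosing day, and SAP 7.11.1 lists itraconazole alone as a regimen. The TAK-954-only reading rests on SAP 4.4, which runs blood sampling to 120 h after the last dose of trial drug in each period. That fits the Day 4 infusion (Day 4 + 5 = Day 9, the end of Period 2) but not the Day 8 itraconazole dose (Day 8 + 5 = Day 13).

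**Scale**
- Share of the SAP's TEAE window from Period 2 Day 1, in calendar days: Days 1 to 3 of 37 = 3/37 = 8.1%.
- Share of routine collection from Period 2 Day 1, in elapsed days: 7 + 10 = 17 to 7 + 14 = 21 days, so 3.04/21 = 14.5% to 3.04/17 = 17.9%.
- One subject of 10 moved between columns: 1/10 = 10 percentage points.

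The first two are shares of time. The documents give no event rate, so they do not estimate the share of events misassigned.

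**The case against.** The best defence is that the intent is plain. The three regimens are named directly after the rule, and in a fixed sequence itraconazole alone can only mean Period 2 before the infusion. A programmer could infer the split, so this is an incomplete sentence and not a wrong analysis. The inference is reasonable, but it means overriding the written rule. Two programmers could then produce different tables, and in an open-label trial (Protocol 8.1.3) the choice might be made after the events are known.

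It can also be said that itraconazole alone is not itself an objective, and that on the more natural reading the TAK-954-alone column is unaffected. Both points stand. On that reading the damage is that about three days of pre-infusion events enter the combination column, and that a required column cannot be filled for infused subjects. Contamination of TAK-954 alone depends on the weaker reading.

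Finally, nothing irrecoverable happens: "Data listings will be provided for all TEAEs", and SAP 7.7 lists dosing times, so each event can be reassigned by hand. That stands as well and limits the severity, but it does not make the summary tables right.

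**Conclusion.** The concern holds. Followed literally, the rule labels 0 of the 73 pre-infusion hours as itraconazole alone for any subject infused on Period 2 Day 4, on either meaning of study drug. No other section of the protocol or SAP splits Period 2 at the infusion. The result assumes nominal dosing times and, for the 37-day window, itraconazole through Day 8.

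This should be corrected, but its reach is modest. It affects descriptive safety tables that serve the secondary objective. No test is applied to them, and the primary comparison of Cmax and AUC∞ does not depend on them.

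**What to change.** In SAP 7.11.1, state that study drug for TEAE purposes means both TAK-954 and itraconazole, and assign events by dose time:

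- **TAK-954 alone:** onset from the start of the Period 1 infusion to just before the first itraconazole dose.
- **Itraconazole alone:** onset from the first itraconazole dose to just before the start of the Period 2 Day 4 infusion.
- **TAK-954 with itraconazole:** onset from the start of that infusion onward.

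Each window should end at the next listed dose or, if that dose is never given, at the existing 30-day limit. By the SAP's own formula that limit is Period 1 Day 30 for a subject dosed only in Period 1 (1 + 29). It is Period 2 Day 30 to 33 when the last dose is itraconazole on Day 1 to 4 with no infusion (1 + 29 to 4 + 29), and Period 2 Day 37 for dosing through Day 8.

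Because SAP 7.1.4 does not impute incomplete event dates, add a tie rule for an onset on Period 2 Day 1 or Day 4 that has a date but no time. One option is Day 1 to itraconazole alone and Day 4 to the combination, with a flag in the listing.

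The cost is a few sentences. Event start times (Protocol 10.2.9.2) and dosing times (SAP 7.7) are already recorded, so no new data, extra table or protocol change is needed.

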3.0 SCHEDULE OF TRIAL PROCEDURES

Assessment	Screening	Trial Period 1 (a)						Trial Period 2							Follow-up/Early Termination		
		Day	-28 to -2	-1	1	2	3	4 to 6	-1	1	2 to 3	4	5	6	7	8	9
Administrative Procedures																	10-14 days after last dose of trial drug
Informed consent	X																
Inclusion/exclusion criteria	X	X															
Medical history/demographics	X																
Prior and concomitant medication review			-----Continuous review-----														
Clinic Procedures/Assessments																	
Full physical examination	X	X															X
Semirecumbent vital signs (heart rate [HR], systolic blood pressure [SBP] and diastolic blood pressure [DBP])	X		X(b)	X	X			X	X	X	X	X	X			X	X
Vital signs (respiratory rate, oral [at the floor of the mouth]/tympanic temperature) rate	X		X(b)					X									
Height	X																
Weight	X																
Body mass index (BMI)	X																
Standard 12-lead electrocardiogram (ECG)	X		X(b)		X		X				X				X		X
CCI																	
Adverse event (AE) monitoring			-----Continuous review-----														
Laboratory Procedures/Assessments																	
Serum chemistry	X	X			X		X							X			X
Hematology	X	X			X		X							X			X
Urinalysis	X	X			X		X						X			X	
Serum follicle-stimulating	X																

CONFIDENTIAL

Assessment	Screening	Trial Period 1 (a)						Trial Period 2						Follow-up/Early Termination		
		-28 to -2	-1	1	2	3	4 to 6	-1	1	2 to 3	4	5	6	7	8	9
Day	-28 to -2	-1	1	2	3	4 to 6	-1	1	2 to 3	4	5	6	7	8	9	10-14 days after last dose of trial drug
hormone (FSH)																
Urine drug screen	X	X					X									
Urine alcohol test/alcohol breath test (d)	X	X					X									
HIV test	X															
Hepatitis panel	X															
Pharmacokinetics (PK) Evaluations																
Plasma samples for TAK-954 (e)			X	X	X	X				X	X	X	X	X	X	
Urine sample for TAK-954 PK (f)			X	X	X					X	X	X				
Pharmacogenomic (PGx) Evaluations																
Blood sample for DNA PGx			X													
Blood sample for RNA PGx			X													
Drug Administration																
TAK-954 dosing			X								X					
Itraconazole dosing								X	X	X	X	X	X	X		
Other																
Confinement		X	X	X	X			X	X	X	X	X	X	X		
Meals		X	X	X	X			X	X	X	X	X	X	X		

(a) A minimum of 7 days between doses in Period 1 Day 1 and Period 2 Day 1.

(b) Assessments at predose (within 30 minutes), 1, 2, 4, 8, and 12 hours postdose (relative to TAK-954 start of infusion).

(c) CCI

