10.2.9 Collection and Reporting of AEs, SAEs, and Abnormal LFTs

10.2.9.1 Collection Period

Collection of AEs (ie, AEs, SAEs, and abnormal LFTs) will commence at the time the subject signs the informed consent. Routine collection of AEs will continue until the Follow-up Visit 10-14 days after the last dose of trial drug. For subjects who discontinue before the administration of trial medication, AEs will be followed until the subject discontinues trial participation.

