10.2.9.3 Reporting SAEs

When an SAE occurs through the AE collection period it should be reported according to the procedure outlined below:

A Takeda SAE form must be completed, in English and signed by the investigator immediately or within 24 hours of first onset or notification of the event. The information should be completed as fully as possible but contain, at a minimum:

- A short description of the event and the reason why the event is categorized as serious.
- Subject identification number.
- Investigator's name.
- Name of the trial medication(s).
- Causality assessment.

The SAE form should be transmitted within 24 hours to the attention of the contact listed in Section 14.1.1.

Any SAE spontaneously reported to the investigator after the AE collection period should be reported to the sponsor if considered related to trial participation.

Reporting of SAEs that begin before the first administration of investigational product will follow the same procedure for SAEs occurring on treatment.

SAE Follow-up

If information is not available at the time of the first report becomes available at a later date, the investigator should complete a follow-up SAE form or provide other written documentation and fax it immediately within 24 hours of receipt. Copies of any relevant data from the hospital notes (eg, ECGs, laboratory tests, discharge summary, postmortem results) should be sent to the addressee, if requested.

All SAEs should be followed up until resolution or permanent outcome of the event. The timelines and procedure for follow-up reports are the same as those for the initial report.

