11.1.4.1 AEs

All AEs will be coded by system organ class (SOC) and preferred term (PT) using the Medical Dictionary for Regulatory Activities (MedDRA). Treatment-emergent adverse events (TEAEs) with onset occurring within 30 days (onset date minus last date of dose $+1 \leq 30$) after the last dose of trial drug will be included in the summary tables. All AEs will be in the listings. TEAEs will be summarized by SOC and PT. The following summary tables will be included in the report: summary of TEAEs and drug-related AEs, relationship of AEs to trial drug (related vs not related), severity of AEs, and related SAEs. Data listings will be provided for all AEs including TEAEs, AEs leading to trial drug discontinuation, and SAEs.

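### By-regimen TEAE percentages compare at least 7 days on TAK-954 alone with 14-18 observed days on the combination; add a table with equal windows

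*SAP*

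**What the plan says.** SAP 7.11.1 assigns a TEAE to a regimen if it starts after dosing in a period and "up to just prior to study drug administration in the next period". For the final period, an event after dosing and "up to 30 days after the last study drug dose is attributed to the regimen received in the last period". Protocol 11.1.4.1 uses the same limit, including TEAEs "with onset occurring within 30 days" of the last dose.

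The gap between periods has only a lower bound in the Protocol 3.0 schedule, footnote (a): "A minimum of 7 days between doses in Period 1 Day 1 and Period 2 Day 1". In Period 2, itraconazole is given on Days 1 to 8 and TAK-954 on Day 4 (Protocol 9.4, SAP 4.4).

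Protocol 10.2.9.1 says: "Routine collection of AEs will continue until the Follow-up Visit 10-14 days after the last dose of trial drug". For later events, Protocol 10.2.9.3 adds: "Any SAE spontaneously reported to the investigator after the AE collection period should be reported to the sponsor if considered related to trial participation".

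The tables show number and percentage of subjects for three regimens (TAK-954 alone, itraconazole alone, TAK-954 with itraconazole) and overall. No adjustment for observation time is stated, and no rule divides Period 2 between its two regimens.

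**The concern.** The secondary objective is the safety of TAK-954 with and without the inhibitor, and the by-regimen TEAE tables are the main AE summary for it. A subject counts once per term however long the regimen is watched, so the percentage rises with the length of the window even when the event rate is the same. If the combination is watched longer, its column will tend to show more subjects with events although itraconazole changes nothing. With about 10 subjects, one or two extra subjects could be read as an interaction effect on safety.

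**Working it through.** **The plan's own total first.** The Protocol summary gives a period of evaluation of about 7 to 8 weeks. Adding the longest screening (28 days), the minimum interval between Period 1 Day 1 and Period 2 Day 1 (7), Period 2 Day 1 to Day 8 (7) and follow-up (10-14) gives:

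- 28 + 7 + 7 + 10 = 52 days (7.4 weeks)
- 28 + 7 + 7 + 14 = 56 days (8.0 weeks)

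The stated total is reproduced. With full screening, 56 days leaves an interval of 56 − 28 − 7 − 14 = 7 to 56 − 28 − 7 − 10 = 11 days. Shorter screening allows a longer interval.

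**Observed windows**, in elapsed days:

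- TAK-954 alone: Period 1 Day 1 to the first Period 2 dose, at least 7 days.
- Combination, taken from the Day 4 infusion: the last dose is on Day 8, so follow-up falls on Day 8 + 10 = 18 to Day 8 + 14 = 22. The window is 18 − 4 = 14 to 22 − 4 = 18 days.
- Itraconazole alone: Period 2 Day 1 to Day 4, 3 days.

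**Ratio**, combination window divided by TAK-954-alone window:

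| Interval (days) | Follow-up at 10 days | Follow-up at 14 days |
|---|---|---|
| 7 | 14/7 = 2.00 | 18/7 = 2.57 |
| 8 | 1.75 | 2.25 |
| 9 | 1.56 | 2.00 |
| 11 | 1.27 | 1.64 |
| 14 | 1.00 | 1.29 |
| 18 | 0.78 | 1.00 |

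Starting the combination at Day 4 is a reading, because the SAP assigns events by period. If all of Period 2 counted as one regimen, the window would be 17-21 days and the ratio at 7 days 2.43-3.0.

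**Effect on crude percentages.** Assumption, not in the documents: a constant event rate, the same under both regimens, of 1-2% per day. Expected proportion with an event = 1 − exp(−rate × days), at the 7-day interval:

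| Rate per day | 7 days (TAK-954 alone) | 14 days | 18 days |
|---|---|---|---|
| 1% | 7% | 13% | 16% |
| 2% | 13% | 24% | 30% |

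In 10 subjects this is about 0.7 against 1.3-1.6 subjects at 1% per day, and 1.3 against 2.4-3.0 at 2%.

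**The 30-day limit.** The SAP formula counts the last-dose day as 1, so the limit is Day 8 + 29 = Day 37. Routine collection stops 15-19 days earlier, on Day 18-22. After that, only spontaneously reported SAEs considered related to trial participation must be reported.

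**With a matched window.** Seven days after each infusion gives 7/7 = 1.0. In Period 2 it runs from Day 4 to Day 11, before the earliest Follow-up Visit on Day 18.

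**The case against.** Safety is purely descriptive: no test, estimate or decision rule rests on these percentages. The SAP also plans tables of drug-related TEAEs and full listings, and AE start times are recorded (Protocol 10.2.9.2), so a careful reader can separate late or unrelated events. Part of the longer combination window is real exposure, because itraconazole continues to Day 8. A constant daily rate is also a simplification: after the Period 2 Day 9 visit there is no scheduled contact until follow-up, so detection is probably thinner there. All of this stands. It limits the consequence, but does not make the columns comparable.

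A reader might infer three stronger points that the documents do not support:

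- **The combination window is at least twice as long.** Seven days is the minimum for TAK-954 alone, so it gives the largest ratio for a given follow-up, not the smallest. The ratio falls below 2 once the interval exceeds 7 days (10-day follow-up) or 9 days (14-day follow-up).
- **The imbalance is 4.7-fold** (33/7, counting to Day 37). That treats the days after the Follow-up Visit as observed, and they are not routinely observed.
- **The 30-day limit is itself an error and should be cut back to the Follow-up Visit.** It is an inclusion cut-off and makes no claim of complete 30-day ascertainment. It keeps late, spontaneously reported related SAEs in the TEAE tables. Shortening it would change almost no count and could drop exactly those events.

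**Conclusion.** The concern holds as a tilt in a descriptive table. At the minimum interval the combination is observed about 2.0-2.6 times as long as TAK-954 alone, and no stated adjustment allows for it. The tilt shrinks as the interval lengthens. It disappears at 14-18 days, depending on the follow-up day, and beyond that it reverses; the documents set no maximum interval.

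The size in subjects depends on the assumed 1-2% daily rate and on starting the combination at Day 4. The missing rule for dividing Period 2 is a gap on any reading, since the tables need three columns from two periods. This is worth correcting because correction is cheap; it does not threaten the primary PK conclusion.

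**What to change.** In SAP 7.11.1:

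1. Keep the 30-day TEAE definition. Add a table note that routine ascertainment ends at the Follow-up Visit, 10-14 days after the last dose.
2. State that Period 2 events before the Day 4 infusion belong to itraconazole alone, and events from that infusion onward to the combination.
3. For TAK-954 alone against the combination, add a by-regimen TEAE table with the same window after each infusion. Seven days is one choice: Period 1 Day 1 up to the first Period 2 dose, capped at 7 days, and Period 2 Day 4 to Day 11.
4. Show later events in the overall column and the listings.

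This uses onset dates and times already collected and needs no new visit. The cost is one derivation flag and one table, and late-onset events fall outside the matched comparison. Equal windows do not equalise everything: confinement runs to Day 3 in Period 1 but to Day 7 in Period 2, so some difference in detection remains and should be noted.

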7.11.2 Clinical Laboratory Evaluations

Clinical safety laboratory tests for this study are listed below. The schedule of clinical laboratory collections is presented in [Appendix A](#).

Individual results for hematology and chemistry laboratory tests that meet the Takeda predefined laboratory markedly abnormal value (MAV) criteria in [Appendix B](#) will be presented in a data listing. If a subject has a MAV for a particular laboratory test, all visits for that subject for that parameter will be listed.

All clinical laboratory data will be presented in both SI and conventional units in the data listings. Laboratory data outside of the normal reference range will be listed. Out of normal range values and MAVs will be flagged in data listings.

Chemistry

Chemistry evaluations will consist of the following standard chemistry panel:

Albumin	Alkaline phosphatase
ALT	AST
Blood urea nitrogen	Calcium
Bicarbonate	Chloride
Creatinine	Glucose
Gamma-glutamyl transferase	Sodium
Potassium	Bilirubin (total), if above ULN, will be fractionated
Protein (total)	

Hematology

Hematology will consist of the following tests:

Erythrocytes (red blood cells [RBCs])	Hemoglobin
Hematocrit	Platelets
Leukocytes (white blood cells [WBCs]) with absolute differential	

Urinalysis

Urinalysis will consist of the following tests:

Protein	Glucose
Blood	Nitrite

